#### **5.4.2.3. Time to Event Endpoints**

The Kaplan-Meier method will be used to estimate and plot the cumulative incidence by each intervention arm. The log-rank test will be performed to compare between the intervention arms. The median time with 90% CI will be estimated using Kaplan-Meier method. To explore the impact of selected baseline factors in addition of study intervention, the survival probabilities will be estimated based on a stratified Cox regression model including study intervention arm, and each baseline factor at a time with the intervention arm-by-baseline factor interaction term. The strata in the stratified Cox model are the 2 randomization stratification factors to allow for a separate baseline hazard for each level of those factors. The interaction between study intervention arm and baseline/disease characteristic will be explored graphically.

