4.2. Scientific Rationale for Study Design

Randomization

Randomization will be used to minimize bias in the assignment of participants to intervention arms, to increase the likelihood that known and unknown participant attributes (eg, demographic and baseline characteristics) are evenly balanced across treatment arms, and to enhance the validity of statistical comparisons across intervention arms. Randomization will occur at baseline.

Stratification Factors

Randomization will be stratified by absolute HBsAg level (<1,000 IU/mL versus \geq 1,000 IU/mL) at baseline and country grouping as proxy for HBV GT at enrollment, with 3 levels: Poland (predominantly GT-A) versus Russia (predominantly GT-D) versus all other countries (other or mixed GT prevalence) (Kim 2011). The two stratification factors selected will provide a reasonably balanced representation of 2 baseline factors across all intervention arms.

Addition of PegIFN- α 2a to Treatment Regimen

The combination of the treatment regimen of JNJ-3989 + NA with PegIFN- α 2a is based on 2 different properties of IFN- α : a direct antiviral effect and an immune boosting effect. The direct antiviral activity against HBV replication, and in some cases HBsAg production, was demonstrated for PegIFN- α 2a (Belloni 2012, Lucifora 2014, Xu 2010, Yan 2015). In addition, IFN- α is expected to act as immune booster with potential to reactivate NK-cells (Gill 2016). Addition of PegIFN- α 2a (for 12 weeks [during the first or second half of the treatment period for Arms 3 and 2, respectively] or during the complete 24 week treatment period [Arm 1]) to the treatment regimen is expected to enhance antiviral activity of JNJ-3989 + NA and may lead to a shorter overall treatment duration (ie, 24 weeks) and might improve functional cure rates.

Criteria for NA Treatment Completion

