**Figure 1: Schematic Overview of the Study**

ALT: alanine aminotransferase; DNA: deoxyribonucleic acid; EOS: end of study; EOSI: end of study intervention; FU: follow-up; HBeAg: hepatitis B e antigen; HBV: hepatitis B virus; JNJ-3989: JNJ-73763989; N: number of participants; NA: nucleos(t)ide analog; PegIFN-α2a: pegylated interferon alpha-2a; Q4W: every 4 weeks; QD: once daily; QW: once weekly; Rand: randomization.

a If all of the NA treatment completion criteria (see Clinical Protocol Section 6.5.1, NA Treatment Completion, for more details) are met based on the Week 24 results, NA will be stopped at the next scheduled visit (ie, FU Week 2), otherwise NA treatment will continue during the complete FU period.

*Note:* Participants who are close to meeting the protocol-defined NA treatment completion criteria with the Week 24 results, and do meet the criteria based on the FU Week 2 results may be allowed to stop NA at FU Week 4, after consultation with the Sponsor.

Participants who meet the protocol-defined NA treatment completion criteria will be monitored closely during the 48-week FU Period with a study visit at least once every 4 weeks. NA treatment should be re-started in accordance with the NA re-treatment criteria are met (see Clinical Protocol Section 6.5.2, NA Re-treatment Criteria During Follow-up, for more details).

At baseline, participants who meet the eligibility criteria will be randomized in a 1:1:1 ratio to Arm 1, Arm 2, or Arm 3. Randomization will be stratified by absolute HBsAg level (<1,000 IU/mL versus ≥1,000 IU/mL) at baseline and country grouping as proxy for HBV genotype (GT) at enrollment, with 3 levels: Poland (predominantly GT-A) versus Russia (predominantly GT-D) versus all other countries (other or mixed GT prevalence). Participants in Arm 2 who no longer meet the PegIFN-α2a eligibility criteria (see Exclusion Criterion A24 in Clinical Protocol Section 5.2, Exclusion Criteria) at Week 12, based on available laboratory or clinical data, will continue JNJ-3989 and NA treatment until Week 24 without PegIFN-α2a.

All participants will receive the last dose of JNJ-3989 at Week 24 and the last dose of PegIFN-α2a at Week 23 (Arms 1 and 2) or Week 11 (Arm 3). They will start the FU period after the Week 24 visit. If the protocol-defined NA treatment completion criteria (Section 5.4.1.1.1) are met based on the Week 24 results, treatment with NA will be stopped at the next scheduled visit (ie, FU

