### **5.1.7. Level of Significance**

For the primary efficacy endpoint analysis, the statistical comparison will be conducted using an exact binomial test against a fixed external control value of 2% at a one-sided Type 1 error rate of 0.05 and applying the Hochberg procedure for adjusting for multiple comparisons. For the comparisons between the intervention arms (Arms 1,2,3), the Mantel-Haenszel test adjusting for the stratification factors will be used in a secondary analysis to compare the primary endpoint between the intervention arms at a one-sided alpha level of 0.05 and applying the Hochberg procedure for multiple comparisons adjustment.

For all other efficacy analyses, only two-sided 90% CIs will be provided with no adjustment for multiplicity, unless otherwise specified.

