#### **5.4.2. Analysis Methods**

Summaries and graphs will be provided for each intervention arm and analysis phase, unless specified otherwise.

Statistical comparisons of the secondary endpoints among intervention arms will be done with no adjustment for multiplicity.

All secondary endpoints will be analyzed based on the observed case data. Additional analyses with specific imputation methods for missing data are added for selected endpoints.

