### **5.5.2.3. Time to Event Endpoints**

The time-to-event endpoints will be analyzed in a similar manner as for the time-to-event endpoints described in Section 5.4.2.3.

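### The between-arm log-rank test for time-to-event endpoints ignores the randomisation strata; stratifying it, HBsAg first, is a cheap improvement whose benefit depends on how prognostic baseline HBsAg is

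*SAP*

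**What the plan says.** SAP 5.4.2.3 plans Kaplan-Meier curves by arm ("The Kaplan-Meier method will be used to estimate and plot the cumulative incidence by each intervention arm") and one between-arm test: "The log-rank test will be performed to compare between the intervention arms". It gives no strata, sidedness, level, or choice between a global and a pairwise test. SAP 5.5.2.3 carries the method to the exploratory endpoints: "The time-to-event endpoints will be analyzed in a similar manner".

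The design is stratified. SAP 1.2 states "Randomization will be stratified by absolute HBsAg level (<1,000 IU/mL versus ≥1,000 IU/mL) at baseline and country grouping", with three country groups, and Protocol 6.3 specifies permuted blocks. That makes 2 × 3 = 6 strata.

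Other between-arm analyses in the SAP use these factors:
- For the primary endpoint, SAP 5.1.7 says "the Mantel-Haenszel test adjusting for the stratification factors will be used in a secondary analysis"; SAP 5.3.2.1.1.2 repeats this.
- The MMRM in SAP 5.4.2.2.1 includes both factors as fixed effects.
- Later in SAP 5.4.2.3 itself, for a Cox model: "The strata in the stratified Cox model are the 2 randomization stratification factors".

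The status of these comparisons is also clear. SAP 5.4.2 says "Statistical comparisons of the secondary endpoints among intervention arms will be done with no adjustment for multiplicity", and SAP 5.5.2 says the same for exploratory endpoints.

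**The concern.** The log-rank test is the only between-arm test named for these endpoints, and it treats blocked data as unblocked. The Cox model does not replace it: it takes one baseline factor at a time, with an arm-by-factor interaction, to explore those factors.

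If a stratum is prognostic, two things happen. Stratified assignment removes the between-stratum part of chance imbalance, but the unstratified variance still counts it, so the test rejects too rarely under the null. Mixing fast and slow strata also pulls the marginal treatment contrast towards 1. At stake is the ability to separate the PegIFN-α2a schedules on time to HBsAg milestones, with 34 per arm.

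**Working it through.** **1. The plan's own between-arm power.** No power is stated for any log-rank test. The only between-arm figure is about 68% for the binary Week 24 endpoint (SAP 3): 50% vs 80%, one-sided 0.05 with Hochberg. At the strictest Hochberg step, α = 0.05/3, with n = 34 per arm:

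power = Φ{[0.30 − z·√(2·0.65·0.35/34)] / √((0.25+0.16)/34)}, z = 2.128

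= Φ{(0.30 − 2.128 × 0.1157)/0.1098} = Φ(0.49) ≈ 68.8%. The figure reproduces.

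**2. The two tests.** At each event time, with d events, n at risk and n₁ at risk in arm 1, U = Σ(d₁ − d·n₁/n) and V = Σ d(n₁/n)(1 − n₁/n)(n − d)/(n − 1). The unstratified test is U/√V over everyone. The stratified test is ΣU_k/√ΣV_k over strata k.

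**3. Is the HBsAg stratum likely to be prognostic?** This depends on the endpoint (SAP 5.4.1.3). Entry requires HBsAg >5 IU/mL at screening (Protocol 5.1, A13.1).
- *HBsAg <100 IU/mL:* log10(1,000/100) = 1. A low-stratum participant needs a fall of less than 1 log, and some may start below 100. Every high-stratum participant needs more than 1 log.
- *Seroclearance (<0.05 IU/mL):* log10(5/0.05) = 2.0 and log10(1,000/0.05) = 4.3. The low stratum needs roughly 2.0 to 4.3 log, the high stratum more than 4.3.
- *Declines of ≥1, 2 or 3 log10:* relative to baseline, so no such direct dependence.
- *Breakthrough, flares, HBV DNA <LLOQ:* not HBsAg-level endpoints.

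**4. Simulated power.** 34 vs 34, assignment balanced within 6 strata, one-sided 0.05, exponential times read at scheduled visits. Treatment HR, event rates, stratum HR and stratum sizes are all assumptions. Monte Carlo error is about 1 to 1.5 points.

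| Horizon; treatment HR | Control events | Stratum HR | Unstratified | HBsAg-only strata | 6 strata | Gain (6 strata) |
|---|---|---|---|---|---|---|
| Week 24; 2.2 | 51%/88% by HBsAg stratum | 3 | 79% | 88% | 86% | 7 |
| Week 24; 2.2 | 38%/91% | 5 | 66% | 85% | 84% | 18 |
| Week 24; 2.2 | 25%/94% | 10 | 41% | 81% | 79% | 38 |
| Week 72; 2.0 | 50% | 1 | 69.9% | 70.4% | 67.4% | −2.5 |
| Week 72; 2.0 | 50% | 3 | 61.6% | 69.3% | 67.1% | 5.5 |
| Week 72; 2.0 | 50% | 5 | 50.8% | 66.6% | 63.6% | 12.8 |
| Week 72; 2.0 | 50% | 10 | 31.1% | 66.4% | 62.2% | 31.1 |
| Week 72; 2.0 | 30% | 3 | 49.6% | 53.3% | 52.9% | 3.3 |
| Week 72; 2.0 | 30% | 5 | 43.3% | 53.1% | 50.9% | 7.6 |
| Week 72; 2.0 | 30% | 10 | 39.8% | 54.7% | 53.1% | 13.3 |
| Week 72; 2.2 | 20% | 3 | 49.2% | – | 52.5% | 3.3 |
| Week 72; 2.2 | 20% | 5 | 46.6% | – | 50.4% | 3.8 |
| Week 72; 2.2 | 10% | 3 | 31.5% | – | 31.5% | 0 |
| Week 72; 2.2 | 10% | 5 | 31.4% | – | 32.5% | 1.1 |

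A separate Week 24 run with HBsAg-only strata and treatment HR 2.2 gave gains of about 8, 19 and 40 points at stratum HR 3, 5 and 10 with 65% control events. With 20% events the gains were about 3, 5 and 9.

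**5. Type I error of the unstratified test (nominal 5%).** Week 72 runs: 4.6-5.6% with non-prognostic strata, 4.0-4.2% at stratum HR 3, 3.3-4.6% at HR 5, 1.4-2.9% at HR 10. Week 24 runs with common events: 3.2%, 2.7% and 1.4% at HR 3, 5 and 10.

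**6. A run tied to the plan's own rates.** HBsAg declines were calibrated to 50% vs 80% with a ≥2 log fall (SAP 3), with the >5 IU/mL entry floor. Assumed: baseline mean 3.0-3.3 log10, SD 0.7-0.9; SD of decline 0.5-0.8 log10; the shape of the decline. For time to HBsAg <100 IU/mL the implied stratum HR was about 6 to 14. HBsAg-only stratification gained 9 to 21 points (for example 59% to 72%, 26% to 46%) and 6 strata about 7 to 19. Type I error of the unstratified test was 1.3-2.7%.

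**7. Cost when the strata are not prognostic.** Six strata: 0 to 5 points (worst case 83.8% to 78.8%). HBsAg-only: about 0.

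**The case against.** An unstratified log-rank test is valid, does not inflate type I error, and matches the unstratified curves beside it. The marginal contrast it tests is a legitimate target. The stratified Cox model will give some stratum-adjusted results. No decision or power claim rests on these tests, and SAP 5.1.7 limits other efficacy analyses to two-sided 90% CIs unless otherwise specified; the one-sided 0.05 used above is borrowed from the primary-endpoint comparisons.

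All of that stands, and it sets the weight of the point. It does not explain why this one test departs from the randomisation and from the other analyses in the same SAP.

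The objection to a uniform 6-stratum rule also stands. SAP 5.4.1.3.3 restricts time to HBV DNA <LLOQ to NA re-treated participants, a subset in which six strata could be nearly empty.

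A reader might infer that the plan forfeits a fixed amount of power, in the tens of points, on every time-to-event endpoint. The documents do not support that. They give no treatment HR, event rate or prognostic effect for these endpoints. Across the assumptions tried, the change from stratifying by all six strata ran from about −5 to +43 points, the top value needing a stratum HR of 20 with a twofold country effect. The endpoints also differ in how directly starting HBsAg bears on them.

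**Conclusion.** The inconsistency is in the text and the direction of its effect is clear: with a prognostic stratum, the unstratified test is conservative and less powerful. The size depends on assumptions. For 34 vs 34 it is about nil when the stratum is not prognostic or events are uncommon. At a stratum HR of 3 it is about 3 to 8 points, slightly more with HBsAg-only strata and very common events, and less when power is already near its ceiling. It is about 10 to 40 points only when events are common and the stratum HR is about 5 to 10; in those cases type I error is about 1-3%.

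A stratum HR in that upper range is plausible for time to HBsAg <100 IU/mL, but that rests on an assumed baseline distribution. The argument is weaker for log-decline endpoints and is not made for flares or breakthrough.

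The affected comparisons are secondary or exploratory, unpowered and unadjusted. The exact binomial test against 2% and the stratified Mantel-Haenszel comparison are untouched. This is a cheap improvement, not a flaw that threatens the trial's main conclusion.

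**What to change.** In SAP 5.4.2.3, replace the log-rank sentence with:

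*Intervention arms will be compared with a log-rank test stratified by baseline HBsAg (<1,000 / ≥1,000 IU/mL) and country grouping, collapsing over country and retaining HBsAg when a stratum contains no participants from one of the arms compared; analyses restricted to NA re-treated participants (5.4.1.3.3) will be unstratified.*

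SAP 5.5.2.3 inherits this by reference, and the Kaplan-Meier curves stay as planned. The same edit could state the sidedness and level of the test.

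The cost is one sentence and one strata specification in the program, plus about 0 to 5 points of power if the strata prove not to be prognostic (about 0 with HBsAg-only strata). It should be fixed before data are reviewed: the trial is open-label and the study team sees interim results (Protocol 9.5), so a later choice would be post hoc.

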		W0/ D1	W2 ^f	W4	W8	W12	W14 ^g	W16	W20	W24/ EOSI/ WD ^e	FU W2	FU W4	FU W8	FU W12	FU W16	FU W20	FU W24	FU W28	FU W32	FU W36	FU W40	FU W44	FU W48 /EOS /WD ^e	
Visit Day (D)/Week (W)	W 4 to 0 ^e	W0/ D1	W2 ^f	W4	W8	W12	W14 ^g	W16	W20	W24/ EOSI/ WD ^e	FU W2	FU W4	FU W8	FU W12	FU W16	FU W20	FU W24	FU W28	FU W32	FU W36	FU W40	FU W44	FU W48 /EOS /WD ^e	
Study Day (Window)	28 to 0	1	15 +/- 2d	29 +/- 2d	57 +/- 2d	85 +/- 2d	99 +/- 3d	113 +/- 3d	141 +/- 3d	169 +/- 3d	15 +/- 4d	29 +/- 4d	57 +/- 4d	85 +/- 4d	113 +/- 4d	141 +/- 4d	169 +/- 4d	197 +/- 4d	225 +/- 4d	253 +/- 4d	281 +/- 4d	309 +/- 4d	337 +/- 4d	
Testing for hepatitis A, B, C, D, and E virus, HIV 1 and 2 ^{bb}	X																							
Serum IgM anti HBc antibody test	X																							
FSH test (postmenopausal women only) ^{hh}	X																							
AFP test ^{bb,ii}	X									X							X							X
Hemoglobin A1c test	X																							
Serum pregnancy test (women of childbearing potential only)	X																							
Urine pregnancy test (women of childbearing potential) ^{jj}		X		X	X	X		X	X	X		X	X	X	X	X	X	X	X	X	X	X	X	X
TSH and T4	X				X				X															
Efficacy Evaluations																								
Fibroscan ^{kk}		(X)								(X)							(X)							(X)
HBV Virology																								
Blood sampling for HBV DNA ^{ww}	X	X	X	X	X	X	X	X	X	X	X	X	X	X	X	X	X	X	X	X	X	X	X	X
HBV genotype ^{ll}	X	X																						
Blood sampling for HBV RNA ^{mm}	X	X		X	X	X		X	X	X		X		X		X								X
Sampling for viral genome sequencing ⁿⁿ	X	X				X				X				X		X		X		X				X
HBV Serology																								
Blood sampling for:																								
Anti HBs and anti HBe	X	X				X				X		X		X		X			X		X			X
HBsAg and HBeAg (qualitative)	X	X				X			X				X			X			X					X
HBsAg (quantitative)	X	X	X	X	X	X	X	X	X	X	X	X	X	X	X	X	X	X	X	X	X	X	X	X
HBeAg (quantitative)	X					X			X		X	X	X	X	X	X	X	X	X	X	X	X	X	X
HBcrAg ^{mm}	X	X		X	X	X		X	X	X		X		X		X				X				X
Exploratory serology ^{pp}	X	X	X	X	X	X	X	X	X	X	X	X	X	X	X	X	X	X	X	X	X	X	X	X
Clinical Pharmacology Assessments																								
Blood sampling for sparse PK of JNJ 3989, NA and PegIFN α2a ^{qq}		X		X		X		X		X														
Exploratory Host Biomarkers																								
Whole blood RNA gene expression (RNA PAXgene tubes)		X ^{rr}	X	X		X ^{rr}	X	X		X														X

Study Period	Screening	Treatment ^{a,b,c}									Follow-up ^{a,c,d}													

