- d. Visits at follow up Week 8, 16, 20, 28, 32, 40, and 44 are optional for participants who continue NA treatment or have restarted NA treatment during the follow up period (provided that their HBV DNA and ALT values are stable) and mandatory for participants who do not continue NA treatment during the follow up period. Participants who experience

ALT/AST elevations as defined in Section 8.3.6.2, Intervention emergent ALT/AST Elevations, will be monitored on a weekly basis or more frequently until ALT and AST levels have returned to <5x ULN and HBV DNA is <20,000 IU/mL.

- e. If necessary (eg, for operational reasons), the Screening Period may be extended up to a maximum of 8 weeks in agreement with the Sponsor.
- f. Only applicable for participants of Arms 1 and 3.
- g. Only applicable for participants of Arm 2.
- h. Both the Platform Master ICF and the ISA ICF must be signed before the first study related activity.
- i. Minimum criteria for the availability of documentation supporting the eligibility criteria are described in the source documents section in Attachment 3 of the Master Protocol PLATFORMPAHPB2001. Clinical status will be checked and documented at screening and again before first dose of study intervention. If a participant's clinical status changes (including any available laboratory results or receipt of additional medical records) after screening but before the first dose of study intervention is given such that he or she no longer meets all eligibility criteria, then the participant should be excluded from participation in the study.
- j. Only applicable for Arm 2: Exclusion criterion A24 regarding contraindications to the use of PegIFN α 2a needs to be checked and documented again prior to the first dose of PegIFN α 2a on Week 12. If an Arm 2 participant's clinical status changes (including any available laboratory results or receipt of additional medical records) after randomization but before the first dose of PegIFN α 2a is administered, such that he or she meets exclusion criterion A24, then the participant will continue treatment as planned but without PegIFN α 2a (ie, JNJ 3989+NA until Week 24).

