## 5.1.3. Visit Windows

As participants do not always adhere to the protocol visit schedule, the following rules are applied to assign actual visits to analysis visits. All visits for all assessments (safety, efficacy or PK) will be uniquely allocated within each phase to an analysis time point based on the analysis relative day (ADY) compared with the target day based on [Table 4](#). All assignments will be made in chronological order. Once a visit date is assigned to a visit window, it will no longer be used for a later time point except for the end of treatment period and end of study (EOS) visits. If a participant has 2 or more actual visits in 1 visit window, the visit closest to the target day will be used as the protocol visit for that visit window. The other additional visit(s) will not be used in the summaries or analyses, but they can be used for determination of clinically important endpoints. If 2 actual visits are equidistant from the target day within a visit window, the later visit is used. If there are two or more measurements on the same day, then the last measurement in chronological order will be used. If the time of the assessment is not available, the highest record/sequence number will be selected.

The listings will include all measurements, also those multiple assessments with the same visit window/phase.

End of treatment (EOT) and end of study (EOS) time points will be included in all analyses over time unless otherwise stated.

Table 4 provides the analysis time points and time intervals for each visit per analysis phase.

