#### **5.4.1.1.4. HBsAg Seroclearance**

Seroclearance of HBsAg is defined as a (quantitative) HBsAg level <LLOQ (see [Table 5](#)). HBsAg seroclearance can be observed prior to the time point assessed but must be observed at the given week of interest.

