## **5.4.1.3. Time to Event Endpoints**

### **5.4.1.3.1. Time to First HBsAg Seroclearance**

Time to HBsAg seroclearance is defined as the number of days between the date of first study intervention intake and the date of the first occurrence of HBsAg seroclearance (i.e. the date of the first HBsAg seroclearance – the date of first study intervention intake + 1). The participants who withdrew early from the study before achieving HBsAg seroclearance or who did not achieve HBsAg seroclearance will be censored at the last available HBsAg assessment.

Time to HBsAg seroclearance will be also analyzed considering the participants who were retreated with NA before achieving HBsAg seroclearance as censored at the date of NA retreatment.

In addition, time to the first occurrence of the following events (i.e. the date of the first occurrence of the event – the date of first study intervention intake + 1) will be analyzed:

- HBsAg <100 IU/mL
- HBsAg decline  $\geq 1.0 \log_{10}$  IU/mL
- HBsAg decline  $\geq 2.0 \log_{10}$  IU/mL
- HBsAg decline  $\geq 3.0 \log_{10}$  IU/mL

Time to the first occurrence of the events above will be also analyzed considering the participants who were retreated with NA before achieving the event as censored at the date of NA retreatment.

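### HBsAg is sampled at Week 2 only in Arms 1 and 3 and at Week 14 only in Arm 2, so between-arm log-rank tests and Kaplan-Meier medians based on first-observed dates carry a local visit-schedule artefact

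*SAP*

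**What the plan says.** The Schedule of Activities (Protocol 1.3) draws quantitative HBsAg, HBV DNA and blood chemistry at every treatment visit, including Weeks 2 and 14. Footnote f limits Week 2: "Only applicable for participants of Arms 1 and 3". Footnote g limits Week 14: "Only applicable for participants of Arm 2".

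SAP 5.4.1.1.4 rests on the quantitative assay: "Seroclearance of HBsAg is defined as a (quantitative) HBsAg level <LLOQ". Samples at those two visits can therefore set an event date. SAP 5.4.1.3.1 adds "time to the first occurrence of the following events", covering HBsAg below 100 IU/mL and declines of at least 1, 2 and 3 log10. All are counted from first intake to the date the criterion is first seen.

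SAP 5.4.2.3 estimates Kaplan-Meier curves and medians by arm and adds "The log-rank test will be performed to compare between the intervention arms". The SAP has no common-visit rule, interval-censored method or sensitivity analysis for the unequal grids. SAP 5.1.7 gives no level or sidedness for the log-rank test; other efficacy analyses get two-sided 90% intervals without multiplicity adjustment.

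**The concern.** The log-rank test and the Kaplan-Meier median treat the recorded date as the event date. The true crossing lies somewhere between the last visit that failed the criterion and the first that met it. When all arms share a grid, this rounding is the same everywhere and largely cancels. Here it does not, because the arms are inspected on different days.

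The placement is awkward. Week 14 falls two weeks after Arm 2 starts PegIFN-α2a, which is where a real effect of delayed interferon would first show. An earlier step in the Arm 2 curve at that point cannot be told apart from the effect of the extra sample. Time to HBsAg seroclearance is a listed secondary endpoint, and on-treatment time to virologic breakthrough and to biochemical flare have the same feature.

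**Working it through.** **The plan's own figure.** No power or error rate is stated for the log-rank tests. The nearest between-arm figure is about 68% power for pairwise comparison of the Week 24 proportion (SAP 3). With 30 per arm, rates 50/80/80% and a pooled two-sample z test, closed-form power is 79.8% at one-sided 0.05, 69.2% at 0.025 and 62.7% at 0.05/3. Simulated power under Hochberg is 67.4 to 68.2% per comparison, so the figure reproduces. It uses neither Week 2 nor Week 14.

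**Dating rule.** HBsAg days on treatment, from Protocol 1.3:
- Arm 2: 29, 57, 85, 99, 113, 141, 169
- Arms 1 and 3: 15, 29, 57, 85, 113, 141, 169

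Recorded day = first scheduled day at or after the true day.
- True day in 86 to 99: Day 99 in Arm 2, Day 113 in Arms 1 and 3. Difference 113 − 99 = 14 days, favouring Arm 2.
- True day in 2 to 15: Day 15 in Arms 1 and 3, Day 29 in Arm 2. Difference 29 − 15 = 14 days, favouring Arms 1 and 3.
- Any other day: same recorded day in all arms.

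**Size of the step.** Assume Weibull times, shape 3, median 16 weeks, identical in both arms: F(t) = 1 − 0.5^((t/16)^3).
- By the Week 14 visit, Arm 2 shows F(14) = 1 − 0.5^0.670 = 37.1%.
- By the same time, Arms 1 and 3 show F(12) = 1 − 0.5^0.422 = 25.4%.
- At Week 16 both show F(16) = 50%.

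Simulation gives 37.1% against 25.5%, then 50.0% in both. The gap opens at Week 14 and closes at Week 16.

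**Log-rank error with no true difference.** 34 per arm, Arm 2 against one of Arms 1 and 3. The event-time distributions and the two-sided 10% level are assumptions. Log-normal times, 6,000 trials per row, Monte Carlo standard error √(0.1 × 0.9/6000) = 0.4 points:

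| Median (days), log-SD | Arm-specific grid | Common grid |
|---|---|---|
| 95, 0.25 | 19.8% | 10.6% |
| 60, 0.5 | 12.2% | 9.8% |
| 95, 0.4 | 11.5% | 10.7% |
| 95, 0.6 | 10.7% | 10.5% |
| 130, 0.4 | 10.4% | 10.4% |

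Repeat runs of the first row gave 19.5 to 21.5%. At a median of 168 days (24 × 7, matching SAP 3's assumption of 50% response at Week 24 in the lowest arm), the arm-specific grid gives 9.5% (log-SD 0.4) and 10.0% (log-SD 0.6).

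Weibull times, 4,000 trials each, one-sided 5% rejection for Arm 2 faster:

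| Shape, median (weeks) | Arm-specific grid | Common grid |
|---|---|---|
| 3, 14 | 10.0% | 4.6% |
| 3, 16 | 6.9% | 5.4% |
| 3, 20 | 5.7% | 5.3% |
| 2, 24 | 4.8% | 4.8% |
| Extreme: half have an event, all in Weeks 12–16 | 19.2% | 5.6% |

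**Medians.** With a true median of 95 days, the observed median in Arm 2 is 10.7 days earlier (log-SD 0.25) or 8.3 days earlier (log-SD 0.4). On a common grid the shift is about zero.

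**The opposite direction.** Entry requires HBsAg above only 5 IU/mL (Protocol 5.1, A13.1), so some participants may already be below 100 IU/mL at baseline. Suppose 20% are, and that they are dated at their first post-baseline visit. By Week 2, 20.7% of Arms 1 and 3 are then recorded against 0% of Arm 2, and the test leans slightly against Arm 2 (mean Z −0.10). With exponential times and a median of 8 weeks, rejection at one-sided 5% is 4.0% for Arm 2 faster and 7.0% for Arm 2 slower.

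**The case against.** The strongest case against acting is that the effect is small and confined to secondary analyses without multiplicity control. Outside tightly clustered events the inflation is about 0 to 2.5 points, and at the plan's own 50% Week 24 rate there is none. The median shift is shorter than the routine four-week visit interval. All of this stands. It limits the point's importance but does not remove the bias, which a common grid eliminates at almost no cost.

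Four stronger readings are tempting, and the documents do not support them.

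- A reader might infer that Arm 2 will look faster in general. Week 2 works the other way, and for early events such as HBsAg below 100 IU/mL it can offset or reverse the lean.
- A reader might take 20% as the expected error rate. It needs events packed around Weeks 12 to 16, and the documents give no event-time distribution to suggest that.
- SAP Table 4 applies its Week 2 and Week 14 windows to all arms ("will be uniquely allocated within each phase to an analysis time point based on the analysis relative day (ADY) compared with the target day"). A reader might infer that Week 14 HBsAg rows for Arms 1 and 3 would be filled by retests for abnormal results. The ALT/AST retest panel in Protocol 8.3.6.2 lists HBV DNA and liver tests but not HBsAg, and the hematology rule in 8.3.6.3 does not specify it. On-time Week 12 (Day 85 ± 2) and Week 16 (Day 113 ± 3) visits fall outside the Day 93 to 106 window. Those HBsAg rows would be nearly empty. The point applies mainly to ALT, HBV DNA and hematology tables.
- A reader might think the trial's main between-arm comparison is compromised. The multiplicity-controlled comparison is the Week 24 proportion by Mantel-Haenszel (SAP 5.3.2.1.1.2), which uses neither visit.

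**Conclusion.** The point holds as a local bias in secondary between-arm time-to-event comparisons. The schedule, the first-observation dating and the ordinary log-rank test are explicit, and nothing in the SAP corrects for the unequal grids.

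Under the assumed distributions and a nominal two-sided 10% test, error is about 10 to 12%, and about 20% only in the tightly clustered case. A visible shift in the median, about 8 to 11 days, requires a true median near Week 13 to 14. The direction depends on when events occur: Weeks 12 to 14 favour Arm 2, and Weeks 0 to 2 favour Arms 1 and 3.

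The exposed endpoints are the HBsAg times in SAP 5.4.1.3.1 and on-treatment time to virologic breakthrough and to biochemical flare. Time to seroconversion is largely unaffected, because anti-HBs is not drawn at Week 2 or Week 14. The 14-day dating differences come straight from the schedule. The error rates and median shifts are illustrations that rest on assumed event times.

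**What to change.** In SAP 5.4.2.3, state that for between-arm comparisons of the HBsAg time-to-event endpoints, and of on-treatment time to virologic breakthrough and biochemical flare, events are dated on scheduled visits common to all arms: Weeks 4, 8, 12, 16, 20 and 24, and the follow-up visits. Alternatively, name an interval-censored test. Choose one before the data are analysed. Keep Week 2 and Week 14 results in within-arm displays.

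With common-visit dating, rejection in the simulations returns to 9.8 to 10.7% at nominal two-sided 10%, and to 4.6 to 5.6% at one-sided 5%.

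Optionally, make the Week 2 window in SAP Table 4 apply only to Arms 1 and 3 and the Week 14 window only to Arm 2, extending the neighbouring windows for the other arms. This matters mainly for the ALT, HBV DNA and hematology by-visit tables.

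The cost is SAP wording and a small programming change, with no new data. The downside is slightly coarser dating: an event first seen at Week 2 or Week 14 moves to Week 4 or Week 16 in the between-arm comparison.
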